## 1.1. IdeS®: An Important New Therapeutic Option for Prevention & Treatment of ABMR

[figure not shown]
IdeS® is an IgG-degrading enzyme of *S.pyogenes* that cleaves all four human subclasses of IgG with strict specificity. IgG degrading activity is a common strategy employed by pathogenic bacteria. IdeS hydrolyzes human IgG in positions 236 and 237 of the lower hinge region of IgG heavy chains. This activity is important since the lower hinge region of IgG is critical for interaction with Fc receptors and complement binding. Thus the proteolytic activity on IgG molecules at this site prevents IgG mediated antibody-dependent cellular cytotoxicity and complement mediated injury to the *S. pyogenes*.

## 1.2. Therapeutic Use of IdeS® for Prevention of Antibody- Mediated Injury

As mentioned above, alloantibodies are a major deterrent to access to and success of life-saving organ transplants. Despite advancements in desensitization, designing efficient and effective means of removal of pathogenic HLA antibodies remains a significant medical challenge. Preliminary data suggests that IdeS® exhibits fast and efficient enzymatic digestion of pathogenic antibodies in animal models of autoimmunity and on human autoantibodies. Data from patients with autoimmune neuromyelitis optica (NMO) shows that the complement activating and ADCC activity of the autoantibody, anti-aquaporin-4, is completely inhibited *in vitro* by IdeS® treatment. In addition, *in vitro* treatment of DSA positive serum from highly-HLA sensitized patients awaiting transplantation show complete inhibition of DSA activity in the solid phase luminex assay (see example in figure 1). The collective data from 12 highly sensitized patients demonstrated that IdeS treatment significantly reduced the reactivity in all tested patient sera to individual MHC class I and II antigens, as well as the reactivity in complement dependent cytotoxicity tests.

**Figure 1**

**Figure 1. Efficacy of IdeS on anti-HLA IgG in serum from a sensitized patient. Graph shows the MFI (Raw) against individual antigens for (upper graph) MHC class-I (A, B and C) and (lower graph) MHC class-II (DP, DQ and DR) after mock (blue) and IdeS (red) treatment. MFI: Mean fluorescent intensity.**

### 1.3. Study Hypothesis

Since alloantibodies are the major mechanism by which allografts are lost and are also exclusionary for transplantation of highly-HLA sensitized patients and that current approaches to desensitization and treatment of ABMR are not sufficient to completely overcome these barriers, an unmet medical need exist to improve the access to and success of renal allografts in sensitized patients. To this end, we hypothesize that the use of IdeS® pre-transplant in HS patients will represent a more robust and complete technique to eliminate DSA from the sera of HS patients. A single dose administration of IdeS® in the pre-operative period to HS patients with positive DSAs and flow cytometry crossmatches will durably eliminate circulating DSAs, allow transplantation to occur without ABMR and, in conjunction with standard desensitization therapy, result in a durable suppression of DSA levels thus eliminating the risk for ABMR.

### 1.4. Rationale for Study

Antibody to HLA antigens has a strong impact on mediation of allograft injury and loss. As depicted in Figure 2 below, pre-formed or *de novo* DSAs activate complement, induce endothelial cell proliferation antigens and mediate ADCC resulting in a progression of allograft dysfunction and loss. More than 5000 renal allografts are lost each year in the U.S., approximately 75-80% to antibody mediated injury. Thus, understanding the pathophysiology of ABMR and B-cell activation are critical to improving the longevity of existing allografts and development of successful strategies for desensitization to prevent ABMR.

**Figure 2**

### Course of Acute and Chronic Antibody-Mediated Allograft Injury

[figure not shown]
[figure not shown]

Figure 2 shows the time course of DSAs, their impact on allograft histology and the eventual progression to allograft failure, leaving the recipient highly HLA sensitized. It is important to point out the multi-faceted ability of DSAs to mediate allograft injury. Many of the pathologic features were once thought to be consequences of CNI toxicity leading to reduced dosing of these critical medications which further accelerated allograft loss. Emerging knowledge in this area is critical for development of newer techniques for suppression of DSA responses.

**Figure 3A**

**Figure 3B**

[figure not shown]

[figure not shown]
Figure 3A & 3B: Figure 3A shows the impact of DSAs on long term allograft survival in patients transplanted in France (Loupy et al, NEJM, 2013). These investigators showed that DSAs have a negative impact on long-term graft survival, but when segregated by ability to activate complement (C1q+ DSAs), the impact was significantly magnified. In fact, those who developed C1q+ DSAs post-transplant has a 12 fold greater risk for allograft loss than C1q- DSA patients. Figure 3B shows the mechanisms of alloantibody injury to grafts which include complement activation endothelial injury through direct actions of alloantibody on ENDATs and ADCC as well as induction of accelerated atherosclerosis in allografts.

Clearly, the most important way to approach antibody mediated allograft injury is through the development of antibody-targeted therapies. This would address all pathogenic mechanism associated with alloantibody and allow grafts to continue functioning for much longer periods of time. This would improve the length and quality of life of allograft recipients and reduce costs to the health care system.

Figure 4A & 4B below show data from our center on the long-term outcomes in patients who experienced ABMR after desensitization v. those who did not.

[figure not shown]
**Figure 4A**

Death Censored Graft Survival by ABMR Status

**Figure 4B**

Death Censored Graft Survival by Treatment Status for ABMR

\* IVIG + RituXimab

\*\* PLEX + IVIG + RituXimab

Figure 4A & 4B. We retrospectively reviewed the outcomes of 226 patients who underwent desensitization with IVIG + Rituximab +/- PLEX at Cedars-Sinai Medical Center. Patients were divided into two groups. Group 1 had no ABMR(80%) while Group 2 experienced ABMR(20%). As can be seen in Figure 3A, the long-term outcomes in HS patients who are ABMR+ are significantly worse than those who were ABMR-. In fact, data for the 5 year outcomes of Group 1 are similar to non-sensitized patients in the UNOS data base. This suggest prevention of ABMR is critical for an excellent long-term outcome of allografts. Assessment of factors associated with risk for ABMR showed that re-transplantation, female gender, ESRD caused by glomerulonephritis and presence of stronger class I and class II DSAs at time of transplant were most important. (Table 1 below). Figure 3B shows the difficulty in treating ABMR after transplant in HS Patients. Patients were treated with IVIG + rituximab or IVIG + rituximab + PLEX. Those treated with IVIG + rituximab did better, but this likely reflects a selection bias as more severe cases were treated with PLEX. Clearly, the most important thing we can accomplish is to develop new strategies to prevent ABMR altogether to allow the long term benefits of transplantation to be manifest in these patients.

**Table 1**  
Characteristics Predisposing to ABMR after Desensitization

Characteristic	No ABMR (n=181)	ABMR (n=45)	P
Age, years	49.2±13.0	41.0±11.4	0.0001
Male sex	54 (29.8)	22 (48.9)	0.015
Deceased donor	121 (66.9)	32 (71.1)	0.584
Race			
Caucasian	78 (43.1)	20 (44.4)	0.870
African American	38 (21.0)	15 (33.3)	0.080
Hispanic	45 (24.9)	6 (13.3)	0.097
Asian	15 (8.3)	2 (4.4)	0.381
Other	5 (2.8)	2 (4.4)	0.559
Primary disease			
Hypertension/diabetes mellitus	84 (30.3)	20 (44.4)	0.812
Glomerulonephritis/vasculitis	53 (27.2)	24 (53.2)	0.002
Congenital cystic/dysplastic	10 (5.5)	2 (4.4)	0.772
Others	43 (23.8)	13 (28.9)	0.475
Unknown	23 (12.7)	3 (6.7)	0.255
Previous transplants			
0	90 (50.0)	9 (20.5)	0.0003
1	68 (37.8)	20 (45.5)	0.397
≥2	22 (12.2)	15 (34.1)	0.0005
Other sensitizing events			
Pregnancy	80 (47.6)	12 (27.9)	0.032
Blood transfusions	92 (54.8)	19 (44.2)	0.301
Time on waitlist (mo)	92.9±49.6	131.3±66.3	0.0004
Time to transplant (mo)	4.0±6.9	3.0±3.7	0.449
PRA % at transplant			
Class I	70.3±44.3	83.11±23.92	0.151
Class II	60.9±34.3	59.5±40.6	0.903
Class I >80%	109 (61.6)	32 (71.1)	0.236
Class II >80%	68 (41.2)	24 (57.1)	0.064
T-cell FCMX (MCS) at transplant	60.2±71.3	130.4±103.9	<0.001
Pronase	31.5±76.1	71.2±90.0	0.019
B-cell FCMX (MCS) at transplant	212.8±143.1	249.4±135.8	0.136
Pronase	145.6±123.6	216.0±109.8	0.007
Positive DSA at transplant, any			
Class I only	44 (24.3)	7 (15.6)	0.208
Class II only	26 (14.4)	5 (11.1)	0.570
Both Class I & Class II	43 (23.7)	28 (62.2)	<0.001
None	68 (37.6)	5 (11.1)	0.0007
HLA Matches			
Zero match	36 (19.9)	14 (31.1)	0.105
1-2 Ag Matches	104 (57.5)	24 (53.3)	0.617
≥3 Ag Matches	41 (22.7)	7 (15.6)	0.297
Induction			
Alemtuzumab	143 (79.0)	41 (91.1)	0.061
Daclizumab	28 (15.5)	3 (6.7)	0.124
Thymoglobulin	6 (3.3)	1 (2.2)	0.704
Simulect/basiliximab	4 (2.2)	0 (0.0)	0.314

## 2. Experience with IdeS® in Humans

In January 2014, Hansa Medical, Lund, Sweden announced the successful completion of a Phase I study of IdeS® use in humans. The phase I study was performed between March 2013 and January 2014 and included 29 healthy subjects. The study was a double blind, placebo-controlled, randomized study who received single ascending intravenous doses of IdeS® or placebo. Five groups were dosed with the highest dose group receiving IdeS doses of 0.24 mg/kg BW (table 2). Study objectives were to evaluate safety, tolerability, pharmacokinetics and IgG-cleaving efficacy of the drug candidate IdeS®. Details of the study are presented below.

[figure not shown]
*Table 2. Dose groups and number of subjects dosed in clinical study 11-HMedIdeS-01*

Dose group	Dose	No of healthy subjects	
		IdeS	Placebo
1	0.010 mg/kg BW	4	2
2	0.010 mg/kg BW	4	2
3	0.040 mg/kg BW	4	2
4	0.12 mg/kg BW	4	1
5	0.24 mg/kg BW	4	2

**Figure 5A**

*Figure 5A. Graph shows the MFI (Raw) against individual antigens for (upper graph) MHC class-I (A, B and C) and (lower graph) MHC class-II (DP, DQ and DR) after mock (blue) and IdeS (red) treatment. MFI: Mean fluorescent intensity.*

## 2.2 Safety

### 2.2.1 Adverse Events

A total of 77 AEs were observed in 24 (82.8%) of the subjects and 39 related AEs were observed in 14 (48.3%) of the subjects. In the 0.01 mg/kg dose group there were 24 AEs (12 related) in seven of the eight subjects, in the 0.04 mg/kg dose group there were 11 AEs (6 related) in the four subjects and in the 0.12 mg/kg dose group there were 7 AEs (2 related) in three of the four subjects. One subject who experienced a probable infusion reaction reported 12 of these AEs. In the Placebo group 14 AEs (7 related) was observed in six of the nine subjects. None of the AEs were reported as serious, met any dose limiting toxicity criteria or lead to withdrawal of study drug. The most commonly reported AE was nasopharyngitis, reported for 50 % (10 out of 20) of the subjects on IdeS and for 67% (6 out of 9) of the subjects on placebo. Headache was reported at nine occasions by seven subjects, all on IdeS. Seven incidences of fatigue were reported by six subjects, five on IdeS and one on placebo.

One subject in the highest dose group experienced a possible infusion reaction 2 minutes before completion of the infusion. Symptoms were sinus tachycardia, pharyngeal oedema, chest discomfort, nasal congestion and flushing. The subject was given 2 mL tavegyl (antihistamine)1 mg/mL i.v. and 2 mL betapred (glucocorticoid) 4 mg/mL i.v. and symptoms resolved within 15 minutes. The IdeS infusion was not interrupted and the subject received a full dose. A similar reaction was experienced in one subject dosed with placebo. This subject had three episodes of tachycardia in connection with dosing and he also had elevated IL-6 levels 6 hours after dosing.

### 2.2.2 Infections

Since IdeS degrades IgG antibodies there was an initial concern that study subjects would have an increased risk of infection. Subjects were screened for inherited immunoglobulin disorders, e.g. IgA deficit, before inclusion in the study. Furthermore, concerns were raised that study subjects could be carriers of subclinical bacterial agents (for example pneumococci) with an increased risk of infection due to reduction of plasma IgG. Therefore, subjects received antibiotic prophylaxis (Spektramox (amoxicillin/clavulanate) tablets (1x1, 500 mg/125 mg) until serum IgG levels had returned to  $\geq 4.5$  g/L. All study subjects complied to the antibiotic treatment and there were no signs of an increasing rate of infections within the study group.

[figure not shown]
### 2.2.3 Pharmacokinetics (PK)

IdeS concentrations in serum were detected by a qualified but not validated LC-MS/MS method based on four peptides derived from IdeS. The analysis was performed at Lund University and serum concentration versus time data was analysed by non-compartmental analysis (NCA). The pharmacokinetic parameters were calculated up to 24 hours post dosing, as the remaining concentrations were around or below the estimated quantitative range of the method and thus had a high degree of uncertainty.

None of the analysed peptides could be detected in the pre-dose samples or in samples from the nine placebo subjects. However, IdeS could be detected in samples from the 20

subjects given IdeS, thereby confirming dosing. The IdeS concentration increased with dose in the dose interval given, 0.01-0.24 mg/kg IdeS and the increase in the serum concentration one minute before end of infusion was dose proportional (figure 6).

[figure not shown]
**Figure 6**

*Figure 6. Comparison of serum IdeS concentration one minute before end of infusion versus dose levels of IdeS (0.01, 0.04, 0.12, and 0.24 mg/kg) (logarithmic scale: circles individual concentrations). Analyte: peptide LFEYFK*

For subjects dosed with 0.12 and 0.24 mg/kg IdeS, in total 10 blood samples were collected up to 1 week post dose. The serum concentration versus time curve could be described by a multi-phase elimination curve (figure 7) and the main fraction of IdeS was eliminated during the first 24 hours post dosing. During the first 6 hours after dosing, the mean half-life was 4.1 ( $\pm 2.6$ ) hours at 0.12 mg/kg and 4.9 ( $\pm 2.8$ ) hours at 0.24 mg/kg. The  $C_{\text{max}}$  was 5.0 ( $\pm 2.5$ ) mg/L at 0.12 mg/kg and 8.3 ( $\pm 3.7$ ) mg/L at 0.24 mg/kg. The  $C_{\text{max}}$  and AUC increased with dose in humans.

**Figure 7**

*Figure 7 Comparison of serum concentration of mean values of four peptides (peptide A: AFPYLSTK, peptide B: A/YVTDSLDSNASIGMK, peptide C: GGIIFDAVFTR and*

*peptide D: LFEYFK) versus time profiles up to 24 hr post dose of IdeS after 15 infusion of 0.12 mg/kg or 0.24 mg/kg IdeS.*

[figure not shown]
## 2.2.4 Pharmacodynamics (PD)

SDS-PAGE analysis revealed that complete conversion of the IgG pool into single cleaved IgG (sIgG) was observed in three out of eight subjects dosed with 0.01 mg/kg BW IdeS. SclgG represents partially cleaved IgG where one of the two IgG heavy chains is cut by IdeS. A minor fraction of sclgG was further converted into F(ab')2- and Fc-fragments in these subjects and a weak reduction in plasma IgG was seen. At the next dose level, 0.04 mg/kg BW, the SDS-PAGE analysis showed partial effect in one subject, intermediate effect in one subject and close to full effect in one subject.

[figure not shown]
The SDS-PAGE analysis of subjects dosed with 0.12 mg/kg BW of IdeS revealed that full or close to full effect was accomplished within 24 hours in all four subjects, i.e. IgG was fully cleaved into F(ab')2- and Fc-fragments (figure 8A and 8B). Furthermore, maximum conversion into F(ab')2- and Fc-fragments was reached six hours after dosing and this was confirmed using the PD-assay which showed that the level of intact IgG (plus sclgG) reached minimum levels six hours after dosing (figure 8). The PD-assay is a validated quantitative sandwich-ELISA based on a Fab-specific capture and an Fc-specific detector that measure intact IgG and sclgG, but not the F(ab')2/Fc-fragments generated through IdeS cleavage.

In subjects dosed with 0.24 mg/kg BW of IdeS the IgG pool was converted into sclgG already during dosing and maximal effect was accomplished 2-6 hours after dosing in all four subjects (see SDS-PAGE in figure 8A and B). Thus, IgG cleavage was more rapid at the highest dose level (i.e. 0.24 mg/kg BW), compared to the lower dose (i.e. 0.12 mg/kg BW). The rapid cleavage of human IgG into F(ab')2 and Fc seen with SDS-PAGE analyses was confirmed with the PD-assay which showed that 2-6 hours after dosing low plateau level was reached at less than 5% remaining IgG and it was concluded that this signal mainly originated from sclgG (figure 8). Newly synthesized intact IgG was again detectable in serum two weeks after dosing in all subjects and after three weeks the level of intact IgG had further increased and constituted the main IgG fraction in serum (figure 9). See figure 10 for a summary of the SDS-PAGE analysis results.

**Figure 8A**

**Figure 8B**

*Figure 8A&B. SDS-PAGE analysis of serum from subjects dosed with A) 0.12 mg/kg and B) 0.24 mg/kg IdeS showing protein banding pattern from pre-dosing and up to 24 h after dosing. Intact IgG and single-cleaved IgG (scIgG), Fc and F(ab')2 are indicated in the figure. A marker containing a mix of human IgG, scIgG, F(ab')2 and Fc was also loaded on the gels (last lane). A comparison of the two dose groups shows that IgG cleavage is more rapid in the higher dose group.*

**Figure 9**

[figure not shown]
501

g(IgG)

Placebo

[figure not shown]
*Figure 9. Serum IgG levels in serum from subjects in the two highest dose groups determined using the ELISA PD method performed by Covance laboratories. A, C & E) 0-64 days. B & D) 0-72 hours.*

**Figure 10A**

*Figure 10A. SDS-PAGE analysis of serum from one subject in the 0.24 mg/kg BW illustrating that newly synthesized IgG can be detected after 14 days and has further increased after three weeks to constitute the main IgG fraction in serum.*

**Figure 10B**

**Figure 10B.** Scoring of the effect A) 2 hours and B) 24 hours after administration of IdeS or placebo. The effect was scored as “No effect”: intact IgG represents the dominating IgG-band, “Partial”: sIgG represents the dominating IgG-band or “Full effect”: sIgG is close to non-detectable as the result of conversion to  $F(ab')_2$  and Fc. A representative SDS-PAGE showing the different categories is incorporated in the figures and the different cleavage products are marked.  
 \*Serum (2 hours) was not available from group 1.

## 2.2.5 Immunogenicity

In the first human IdeS study special precautions were taken to prevent hypersensitivity reactions. IdeS originates from *Streptococcus pyogenes* and it is previously known that a significant proportion of the population has preformed IgG against IdeS (HMed Doc. No. 2012-041). Anti-IdeS IgE ( $>0.10$  kU/L) has not been detected in any individual tested so far. However, it is presumed that individuals with preformed IdeS antibodies of both IgE and IgG type have an increased risk of allergic reactions against IdeS. Therefore, specific in vitro test systems (IdeS-ImmunoCap) for the quantitative measurement of IdeS-specific IgE and IgG antibodies has been developed by Thermo Fisher Scientific, Uppsala, Sweden. The IdeS-ImmunoCap was used to screen study subjects before

inclusion and subjects positive for IgE antibodies were not included in the study. Subjects with elevated IgG antibody titers ( $>15$  mg/L) were also excluded from the first in man study.

A total of 78 subjects were screened in the 11-HMedIdeS-01 study. None of the tested individuals had detectable IgE against IdeS but all tested individuals had detectable IgG. The median level of anti-IdeS IgG was 10.6 mg/L (range 2.1-90.8 mg/L) and 28% of the tested individuals had anti-IdeS IgG titers over 15 mg/L and were excluded from the study. Serum samples from included subjects were analysed for anti-IdeS IgG at the following time points; Day 1 (pre-dose), Day 2 (24 h post dosing), Day 3 (48 h), Day 4 (72 h), Day 7 (1 week), Day 14, (2 weeks), Day 21 (3 weeks), Day 28 (4 weeks) and Day 64 (2 months). The majority of the study subjects (dosed with a single dose of IdeS) responded with an increase of serum anti-IdeS IgG (figure 11). The response was non-detectable one week after dosing but had reached close to peak levels two weeks after dosing. The median pre-dose level (all subjects) of anti-IdeS IgG was 5.3 mg/L (range: 2.0-10.6 mg/L) and at day 14 the median level of all subjects dosed with IdeS was 104 mg/L (range: 3.1-1744 mg/L). Two months after dosing the levels of anti-IdeS IgG had started to decrease in the majority of individuals and the median anti-IdeS IgG level of all subjects dosed with IdeS was 87.8 mg/L (range: 10.5-764 mg/L). Although the individual variation in the magnitude of the anti-IdeS IgG response was large there was clearly a stronger response among the subjects receiving 0.12 or 0.24 mg/kg IdeS compared to subjects receiving 0.01 or 0.04 mg/kg. It can be concluded that the anti-IdeS IgG response is very similar in kinetics and magnitude to the response reported for other drugs of bacterial origin, such as streptokinase and staphylokinase (Collen et al., 1997; Declerck et al., 1994; Mainet et al., 1998).

### Figure 11

[figure not shown]

Figure 11. Anti-IdeS IgG levels in human serum from subjects receiving a single dose, A) 0.01 mg/kg, B) 0.04 mg/kg, C) 0.12 mg/kg and D) 0.24 mg/kg, of IdeS. Day 1 represents the pre-dose

sample. Note the different y-axis scales. The samples were analysed using the IdeS-ImmunoCAP (Thermo Fisher Scientific/Phadia) on a Phadia® 250 instrument. The cut-off (LLOQ) for IgG was 2 mg/L.

### 3 Primary Objectives

This study will be an open label design to assess the efficacy of IdeS® in eliminating DSAs in HS patients who are DSA+ and flow cytometry (FCMX) crossmatch + at time of transplant. Safety determinations will be aimed at assessments of any side effects associated with IdeS® administration and risk for infectious complications associated with IdeS® therapy for prevention of ABMR. Limited efficacy determinations will include incidence of allograft rejection, DSA levels at multiple times post-transplant (Day 0, 30, 90 and 180), determinations of renal function, proteinuria (day 0 through day 30), and pathologic assessments of allograft biopsies at 6M after completion of IdeS® therapy. Patients will be followed and assessed for infectious risk after transplantation as well.

#### 3.1 Major Secondary Objectives

To determine if IdeS® treatment, can prevent or significantly reduce ABMR episodes and C4d deposition in incompatible allografts transplanted to highly-HLA sensitized patients from ~25% to <5% in CMX+ donor-specific antibody (DSA)+ patients. Assess allograft function up to 6 M post-transplant, determine renal function using SCr, MDRD GFR calculations and DSA levels. We will also record any late ABMR episodes after IdeS® therapy. This study protocol is shown in Figure 4.

#### 3.2 Inclusion Criteria

- ✓ End-stage renal disease awaiting transplantation on the UNOS list.
- ✓ No known contraindications for therapy with IVIG10%/Rituximab, plasmapheresis (PLEX) or IdeS®.
- ✓ Age 18-70 years at the time of screening.
- ✓ Calculated PRA (CPRA)≥ 50% demonstrated on 3 consecutive samples, Patient highly-HLA sensitized and a candidate for DD transplantation after desensitization at CSMC.
- ✓ At transplant, patient must have donor-specific antibody/ crossmatch positive (DSA/CMX+) non-HLA identical donor.
- ✓ Pre-transplant vaccination with Streptococcus pneumoniae and Nisseria meningitidis
- ✓ Subject/Parent/Guardian must be able to understand and provide informed consent.

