transplants will have pre-transplant labs for screen ADA, DSAs, FCMX, C3 and C4 obtained as outlined (See Study Protocol in Appendix A). In addition to the standard post-transplant immunosuppressive protocol, all patients will receive 0.24mg/kg IdeS® on day 0 on call to the OR prior to transplant procedure. Pre-medications will be given to patients as a precaution with Solumedrol 40mg IVP, Tylenol 650mg PO and Benadryl 50mg PO to minimize the risk of infusion reactions. Crossmatch and DSA tests will also be assessed on day 1 post-transplant to determine the effect of IdeS®. A protocol biopsy will be performed at 6M to assess the allograft for evidence of ABMR, including C4d staining using Banff 2013 criteria. Since ~25% of HS patients experience ABMR post-transplant and 80% of these ABMR episodes occur in the 1st post-transplant month, we feel the assessment of the potential impact of IdeS® therapy is best assessed in this time period. Patients who have evidence of allograft dysfunction will have non-protocol biopsies for cause. After completion of the IdeS® therapy, patients will be followed up to 6M to assess allograft function and ABMR episodes as well as DSAs. A protocol biopsy will be performed at 6M. The protocol is summarized in Fig. 12.

Figure 12

The entered subjects will be followed to determine if the use of IdeS® for prevention of ABMR in this high risk transplant population is safe and without infectious risks. In addition, we will determine the proportion of who developed evidence of ABMR within 6M of completion of the study. We will assess the transplanted patients to determine the number who sustain a viable and functioning kidney allograft for 6 months. All subjects will be evaluated on an intent-to-treat basis. The subject accrual rate will be limited to no more than five subjects per month in the initial three months to assure safety to all subjects. Repeat laboratories will be performed at the completion of IdeS® therapy to determine effect on levels and correlation with any potential events. A detailed analysis of the study is discussed below.

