## 4.2 Defining the Sensitized Patient

For the purposes of this study, we define HLA sensitization as a patient awaiting kidney transplantation on the UNOS waitlist who has a CPRA of  $\geq 50\%$  who also has demonstrable DSA using luminex bead technology and a history of sensitizing events (previous transplants, blood transfusions and/or pregnancies). These individuals must also have sufficient wait time on the UNOS list to allow for frequent offers with a history of positive crossmatches (DD) or an incompatible (LD) with a positive flow cytometry (FCMX), complement-dependent cytotoxicity (CDC+) crossmatch.

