**Figure 14B**

*Figure 14B: Determining acceptable single antigen bead strength by using the sum of the highest DSA values for class I and class II beads versus BPFXM. ♦ Patients with no ABMR episodes, ■ patients with an ABMR episode within 42 day. ♦ A patient with ABMR within 50 to 200 days and patients with ▲ ABMR episodes after 200 days.*

By using the criteria outlined, 74% (80/108) HS (C PRA>80%) DD recipients treated with desensitization (1/06-12/09) were transplanted. A total of 26% (28/108) patients remained on the waitlist during this period with mCPRA 95. Four of these patients were transplanted in 2010. Of the 80 patients transplanted, 42 (53%) were transplanted with a positive donor specific T and/or B cell flow cytometry XM. A total of 19 (24%) patients experienced ABMR +/- CMR ranging from 3 to 535 days post-transplant with a median of 109 days. Seven of these patients were diagnosed with ABMR +/- CMR within the first 42 days. Two patients were diagnosed with late ABMR +/- CMR at post-transplant days 144 and 249. One of these patients had CMV detected by PCR before the diagnosis of ABMR and one patient had CMV detected by PCR at the time of ABMR diagnosis.. Another patient had Parvovirus B19 positive PCR reaction prior to the diagnosis of ABMR (post-transplant day 535). One patient was noncompliant (post-transplant day 139) and lost the graft. Twenty-eight patients (mCPRA 91) were transplanted with a negative donor specific flow cytometry XM. Pretreatment samples were available for 25 of these 28 patients and showed all pretreatment XMs were negative with the donor samples. Among these 28 patients, none had ABMR and 8 had CMR. The CMR occurred between 15 and 773 days post-transplant with the median time at 58 days. A total of 10 patients received zero HLA ABDR mismatched grafts (mCPRA 90), one had ABMR after 101 days post-transplant and one had CMR at 404 days post-transplant.

[figure not shown]
In this data set of 108 patients, we saw an ABMR rate of 24% using careful selection criteria based on FCMX and DSA data at transplant. When compared a concomitant group of non-sensitized patients transplanted during the same time period (N=190), we saw an ABMR rate of <1% in this non-sensitized, low risk group. Thus ABMR is very rare in non-sensitized patients and in patients who are DSA + but FCMX negative who have received desensitization prior to transplantation.

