#### 4.7 Outcomes of HS Patients vs. Non-Sensitized Patient Cohort

As part of the suggested revisions of this protocol, we have evaluated a group (N=170) of patients who underwent desensitization with IVIG + rituximab and were transplanted (2006-2010). This was compared to a group of non-sensitized patients who were transplanted during the same time period who did not receive IVIG, rituximab or alemtuzumab induction. The patient characteristics are shown in Table 1 below. Briefly, the only significant findings were the higher PRA in the Ritux group, more White (non-Hispanics) in the non-Ritux group, more females in the Ritux group, more lymphocyte depleting agents in the Ritux group and significantly longer dialysis times for the Ritux group. In Table 3, we see the outcomes up to 45 months post-transplant in the two groups. Briefly, there are no significant differences between the two groups in regards to patient and graft survival and infection rates however, there were more rejections in the Ritux group. As previously mentioned, the ABMR rate for sensitized patients (CPRA >80%) was 24% vs. <1% for the non-Ritux group.

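### The ~25% ABMR rate that IdeS is meant to lower has no stated source, and its closest match (24%, CPRA >80%) does not describe the patients this trial enrols

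*Combined protocol and SAP*

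**What the plan says.** Section 3.1 sets the ABMR objective as a reduction "from ~25% to <5% in CMX+ donor-specific antibody (DSA)+ patients". Section 4 repeats the starting rate without a CPRA limit or a source: "Since ~25% of HS patients experience ABMR post-transplant".

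Two entry criteria in Section 3.2 matter here. The first is "Calculated PRA (CPRA)≥ 50% demonstrated on 3 consecutive samples". The second is "At transplant, patient must have donor-specific antibody/ crossmatch positive (DSA/CMX+) non-HLA identical donor". Section 4.2 repeats the 50% threshold in the study's own definition of sensitization. Section 3.3 excludes recipients of living-donor and extended-criteria kidneys.

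The historical cohort is described under Figure 14B in Section 4.4: "74% (80/108) HS (C PRA>80%) DD recipients treated with desensitization (1/06-12/09) were transplanted". Its outcome is: "A total of 19 (24%) patients experienced ABMR +/- CMR ranging from 3 to 535 days post-transplant with a median of 109 days". Section 4.7 ties the rate to the higher threshold again: "the ABMR rate for sensitized patients (CPRA >80%) was 24% vs. <1% for the non-Ritux group".

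Section 7 calls the study exploratory and not powered for efficacy. It still lists a reduction in the number and severity of ABMR episodes among the matters of most importance. No test, alpha level or decision rule uses 25%.

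**The concern.** All 20 patients receive IdeS, so a reduction has meaning only against a historical rate. If that rate belongs to a different population, the gap between it and the trial result mixes a drug effect with a difference in patients.

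A patient with CPRA 55% can enter this trial but could not have been in the cohort that gave 24%. Conversely, a crossmatch-negative patient could be in that cohort but cannot enter this trial. Both features plausibly bear on ABMR risk, and the protocol neither mentions nor adjusts for either difference. What is at stake is how the main efficacy signal is read, not a formal error rate.

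**Working it through.** **Inputs.** Section 4.4 (text under Figure 14B): 80 transplanted, 19 with ABMR; 42 transplanted across a positive flow crossmatch; 28 with a negative crossmatch, no ABMR; 10 with zero-mismatch grafts, 1 ABMR. Table 1: counts by PRA and DSA status in the 226-patient cohort. Section 4: n = 20. Confidence intervals are exact (Clopper-Pearson) 95%.

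**1. The plan's own figure.** 19/80 = 23.75%, which rounds to the stated 24% (CI 14.9-34.6%). The other denominator in that text, 108, gives 19/108 = 17.6% and does not fit.

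**2. Is it the source of 25%?** It is a good match but not the only one. In Table 1, patients with any DSA number 7+5+28 = 40 with ABMR and 44+26+43 = 113 without, so 40/153 = 26.1%. That cohort is not stated to be limited to CPRA above 80%.

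**3. CPRA.** Table 1 denominators, back-calculated from its percentages, are 109/0.616 = 177 and 32/0.711 = 45 for class I, and 68/0.412 = 165 and 24/0.571 = 42 for class II.

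| PRA | >80% | ≤80% | Table 1 p |
|---|---|---|---|
| Class I | 32/141 = 22.7% | 13/81 = 16.0% | 0.236 |
| Class II | 24/92 = 26.1% | 18/115 = 15.7% | 0.064 |

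Both contrasts point to less ABMR at lower PRA. Mean class II PRA does not: 60.9 without ABMR against 59.5 with it (p = 0.903).

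No rate for CPRA 50-80% is given, so I assume a range. Let a share f of the 20 patients have CPRA 50-80% with ABMR rate q, and the rest 23.75%. The reference is then f·q + (1−f)·0.2375.
- f = 10%, q = 20%: 0.020 + 0.21375 = 23.4%.
- f = 50%, q = 5%: 0.025 + 0.11875 = 14.4%.

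**4. Crossmatch.** 42 + 28 + 10 = 80, so the three groups account for the cohort. ABMR in crossmatch-positive patients is 19 − 0 − 1 = 18, so 18/42 = 42.9% (CI 27.7-59.0%). In crossmatch-negative patients it is 0/28 (CI 0-12.3%).

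These events run to day 535, while the trial follows patients for 6 months. The text allows bounds. The median of 19 event times is the tenth, at day 109, so at least 10 events had occurred by then. At most one of those was in the zero-mismatch group, leaving at least 9/42 = 21.4%. Events at days 249 and 535 fall outside 6 months; taking the zero-mismatch event as the one near day 101, at most 16/42 = 38.1% remain.

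**5. Effect on reading the trial.** Below 5% of 20 means 0/20, since 1/20 is exactly 5%. With no drug effect, P(0/20) = (1−p)^20, and P(≤1/20) adds 20p(1−p)^19.

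| Reference p | P(0/20) | P(≤1/20) |
|---|---|---|
| 14.4% (low end, step 3) | 4.5% | 19.6% |
| 21.4% (crossmatch-positive, 6-month lower bound) | 0.8% | 5.2% |
| 23.4% (high end, step 3) | 0.5% | 3.5% |
| 25% (Section 3.1) | 0.3% | 2.4% |
| 38.1% (crossmatch-positive, 6-month upper bound) | <0.01% | 0.09% |

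The exact CI for 0/20 is 0-16.8%. It excludes 25% but not 14.4%.

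**The case against.** The strongest case against making much of this has four parts.

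- **The source is inferred.** Sections 3.1 and 4 do not say where 25% comes from, and Table 1 yields 26.1% for DSA-positive patients, which suits the wording of Section 3.1 as well. This stands. It means the sponsor must state the source, not that the reference is matched.
- **The direction is not shown.** A reader might infer that lower-risk patients are being set against a higher-risk reference, so that the comparison flatters IdeS. The documents do not support that. The Table 1 contrasts are non-significant. They are class-specific: a patient with class I at 95% and class II at 20% counts as low for class II. They have no floor at 50%, and about 30% of that cohort had living donors. Section 1.4 does not name PRA among the leading risk factors. The crossmatch contrast is larger and runs the other way.
- **The opposite inference fails too.** A reader might take 43% as the right reference and call 25% conservative. That figure comes by subtraction, includes late events, and belongs to patients with CPRA above 80%. The 6-month bounds of 21% to 38% lie on both sides of 25%.
- **The trial is exploratory.** No decision rule uses 25%, and 0/20 would be unlikely under most plausible references. This stands and limits the point to interpretation.

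**Conclusion.** The mismatch holds; a claimed direction of bias does not. The closest documented match to 25% comes from patients with CPRA above 80%, of whom 38 of 80 were crossmatch-negative or received zero-mismatch grafts. The trial enrols at CPRA 50% or more and requires a DSA/crossmatch-positive, non-HLA-identical donor.

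On CPRA alone, the reference could fall to between 14.4% and 23.4% under the assumed shares and rates. On crossmatch status alone, it is 43% over the full follow-up and between 21% and 38% within 6 months. The net effect cannot be worked out from the documents.

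A result of 0/20 would look favourable against most of this range. A result of 1/20 is where the reference matters most: the chance of one event or fewer without any drug effect runs from under 0.1% to about 20%.

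This rests on the inference that 25% reflects the 24% cohort, on the three crossmatch groups not overlapping, and on the assumed range for CPRA 50-80%. The source may stand in introductory text that was not available.

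**What to change.** Before any outcome is read:

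1. State the source of 25% in Section 3.1.
2. Re-derive the reference from the centre's records under this trial's criteria: CPRA of 50% or more, deceased donor not of extended criteria, DSA-positive and flow-crossmatch-positive, non-HLA-identical, ABMR within 6 months. Put that figure in Section 3.1 with its exact 95% CI.
3. As a supplement, report trial ABMR by CPRA band (50-80% and above 80%) with exact CIs. This step alone would not be enough, because it leaves the crossmatch mix unmatched.

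Eligibility and treatment do not change. The cost is one records query and one table line, since CPRA is already collected for entry. The stated reference may move up or down, and its uncertainty will be visible; the CPRA bands will be small.
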